Outcome testing will be administered by licensed physical therapists or physical therapist assistants who are blinded to group randomization. Testing will occur before intervention (PRE) and after approximately 4, 8 and 12 weeks of training (4WK [*primary endpoint*], 8WK, 12WK). Each testing session will last approximately 2 hours and may include the following measures:

- Walking capacity testing (*6-minute walk test, primary outcome measure*) involves walking back and forth around two cones, using assistive devices, orthotics, guarding and rest breaks as needed.¹⁴⁸ The distance that the participant is able to walk in six minutes is recorded.
- Walking speed testing (*10-meter walk test*) will be performed with a stopwatch and/or a commercially available electronic walkway.^{146,147} Participants will walk down a hallway and/or electronic walkway, using assistive devices, orthotics and guarding as needed. Each test may be performed twice at comfortable speed and twice as fast as possible.
- Aerobic capacity testing involves respiratory gas measurement (VO₂ and VCO₂) by having the participant breathe through a facemask during an exercise test. This testing will use the same exercise protocol as the stress test above and may be performed simultaneously with the stress test. Peak aerobic capacity is defined as the highest VO₂ measurement achieved during the test. After finishing this test and a rest period, participants may complete a verification phase to help determine whether maximum physiologic capacity (a true VO₂-max) was reached.¹⁵¹ During this verification phase, the participant would be asked to walk as fast as possible for approximately 3 minutes. The treadmill screening test may be repeated at each testing time point to inform speed selection for aerobic capacity testing.
- The metabolic cost of gait is measured by the oxygen consumption rate (VO₂) during gait, with adjustment for walking speed and resting VO₂.⁷⁹ The metabolic cost of gait will be assessed with treadmill walking at approximately the average speed recorded during the 6-minute walk test.
- Daily walking activity assessment involves wearing an activity monitor continuously during waking hours for ≥ 3 days and possibly recording sleep/wake times.¹⁵²⁻¹⁵⁵ The monitor will be worn on the non-paretic leg.

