- The Stroke and Aphasia Quality of Life Scale,^{157,158} Stroke Impact Scale,¹³⁸ EQ-5D and Patient Health Questionnaire¹⁴⁷ are reliable and valid self-report quantitative surveys that include questions about quality of life. One or more of these questionnaires will be used.
- The Global Rating of Change (GROC)¹⁵⁹ is a questionnaire that assesses overall impressions of change in health status from the perspective of the participant. The GROC is a 15 point ordinal scale with -7 indicating "a very great deal worse," 0 indicating "no change," and +7 indicating "a very great deal better". The GROC is not applicable at baseline testing because it measures change only.

Heart rate data may also be recorded during the above testing. If there are any issues with data capture (e.g. equipment malfunction), it is possible that participants could be asked to repeat individual tests as long as it would still be possible to obtain quality data without increasing risk to the participant.

Randomization

Participants will be enrolled after PRE testing and randomized to either HIT or MAT. Randomization will be stratified by site and by baseline walking speed (<0.4 , ≥ 0.4 m/s), to help ensure that groups are balanced within sites and on this critical prognostic factor.^{149,150} Within each stratum, we will randomize in *block sizes of 2 or 4*. Block size will be *randomly permuted* to prevent personnel from being able to predict the last randomization within a block.

Training Intervention Protocols

Common features between protocols. Participants in both groups will be asked to perform 36 training sessions over approximately 12 weeks, with repeated outcome testing after each [12 session / 4 week] block. Target training frequency will be 3 sessions per week. Both groups will train for approximately 45 minutes per session, v.5, 16Mar2021

using orthotic & assistive devices and handrail balance support on the treadmill as needed.¹⁴⁴ Each session will include a 3 minute warm up, 10 min overground training with guarding from a physical therapist, 20 min treadmill training wearing a harness for fall protection, another 10 min overground training and a 2 min cool down. Target heart rates (HRs) will be based on the peak HR from exercise testing, to account for β -blocker medications.¹⁴⁴

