- Anaerobic intensity may be measured by *blood lactate concentration* after the treadmill training portion of one or more sessions, using a finger stick and a point-of-care blood lactate analyzer. Blood lactate accumulation is a key feature of vigorous training intensity that provides a mechanistic basis for expected benefits over moderate intensity. Our preliminary data confirmed that among persons with chronic stroke, the anaerobic threshold still occurs almost exactly at the 60% HR reserve transition point between moderate and vigorous intensity.¹³⁶ Further, we demonstrated that our treadmill HIT protocol elicits a consistent and robust lactate response in this population, which is significantly greater than the null effect elicited by MAT ($p<0.001$; Fig 5). In animal and healthy adult studies, increased blood lactate has been shown to drive skeletal muscle mitochondrial adaptations that increase aerobic capacity,¹⁶⁶ to upregulate neurotrophins that facilitate brain plasticity¹⁶⁷ and to predict greater motor learning when paired with skill practice.¹⁶⁸
- Neuromotor intensity may be measured by *treadmill and over ground training speeds* each session.
- Repetition of practice may be measured by *step counts* during each session, using an activity monitor on the non-paretic leg.^{27,34,35,169,170}

Concurrent outside interventions

To test for other between-group differences during the intervention period that could explain differences in outcomes, we may also assess the following measures:

- Concurrent walking practice may be measured by *step counts outside of training sessions*. Participants would be asked to take an activity monitor home to wear during waking hours throughout study participation.¹⁷¹
- Concurrent therapy may be measured by *any changes in medications* and the *number of sessions of outside therapy (e.g. speech & occupational therapy)*.¹⁵⁶

E.2. Data Analysis and Data Monitoring

General approach

[figure not shown]
The REDCap® web-based system²¹⁷ will be used for data entry and data monitoring. All baseline variables and data on intervention fidelity and concurrent outside interventions will be compared between groups with t-tests and X². The primary analysis will follow *intent-to-treat* methods and any missing data will be handled with the method of maximum likelihood, assuming that patterns of missingness do not violate the missing at random assumption.²¹⁸

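### As defined, daily walking activity can include study training sessions at 4WK and 8WK but not at PRE, and no rule places the wear days or removes session steps

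*Protocol*

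**What the plan says.** **The measure.** Protocol, Blinded Outcome Testing: "Daily walking activity assessment involves wearing an activity monitor continuously during waking hours", for at least three days. The monitor goes on the non-paretic leg. The same section sets the time points: "Testing will occur before intervention (PRE) and after approximately 4, 8 and 12 weeks of training".

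**Training relative to testing.** Protocol, Randomization: "Participants will be enrolled after PRE testing and randomized to either HIT or MAT". No study training can therefore have taken place at PRE. Training Intervention Protocols gives both arms 36 sessions over about 12 weeks, "with repeated outcome testing after each [12 session / 4 week] block". It adds "Target training frequency will be 3 sessions per week" and "Both groups will train for approximately 45 minutes per session". A session is made up of 3 minutes of warm-up, 10 overground, 20 on the treadmill, 10 overground and 2 of cool-down.

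**Step counts elsewhere.** Intervention fidelity measures allows steps to be counted "during each session, using an activity monitor on the non-paretic leg". Concurrent outside interventions allows a take-home monitor to record steps outside sessions. Both are optional, and neither is tied to the daily walking outcome.

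**Status.** The Protocol lists daily walking activity among the outcome measures, and H2a and H2b cover secondary outcomes as well as walking capacity. The SAP (Hypothesis Testing) names four secondary outcomes: comfortable gait speed, fast gait speed, oxygen uptake at the ventilatory threshold and a PROMIS fatigue score. Daily walking activity is not among them.

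**Not stated in either document.** Whether sessions take place on wear days, whether the monitor is worn before or after the testing visit, and whether session steps count.

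**The concern.** A measure of everyday walking should capture what participants do outside the study. Here the definition covers all waking hours, and a session contains 40 minutes of supervised walking practice. Any session on a wear day would be counted as daily walking. That cannot happen at PRE, can happen at 4WK and 8WK, and may not happen at 12WK if the monitor is worn after the last session.

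Two within-arm readings are exposed. The change from PRE to 4WK or 8WK could contain the intervention itself. The 8WK-to-12WK change in the HIT group, which H2a examines for secondary outcomes, could show a fall only because sessions have stopped. Randomization does not protect a time contrast within one arm.

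The investigators already separate steps inside sessions from steps outside them, but only for fidelity and concurrent practice. The outcome definition does not carry that separation over, so three sites may choose wear days differently and the analyst has no rule to apply.

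**Working it through.** The plan gives no figure for this measure that could be reproduced. The arithmetic below only sets a scale, on stated assumptions.

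**Inputs from the documents**
- 3 sessions per week, 36 sessions, about 12 weeks (Training Intervention Protocols).
- Wear of at least 3 days (Blinded Outcome Testing).
- 1,400 steps/day for community-dwelling stroke survivors (Section B), used only for scale.

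**Assumptions**
- Training continues through the wear days, on alternate weekdays.
- Wear days are consecutive.
- A session yields 1,000 to 3,000 steps.

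**Step 1: is there a planned pause?** 36 sessions / 3 per week = 12 weeks, the whole planned training period. At the target frequency the schedule contains no built-in training-free week.

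**Step 2: sessions per worn day.** With sessions on Monday, Wednesday and Friday, the seven possible 3-day windows (starting Monday to Sunday) hold 2, 1, 2, 1, 1, 1 and 1 sessions.
- Mean per window = 9/7 = 1.29.
- Mean per worn day = 1.29/3 = 0.43, which equals 3/7. A 7-day window always holds 3.
- If sessions are bunched (Monday, Tuesday, Thursday, or three days running), a 3-day window can hold none.

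**Step 3: steps added to the within-arm change from PRE.** Added steps/day = steps per session × sessions in window / days in window. Percentages are of 1,400 steps/day.

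| Assumed steps per session | Average (3 sessions in 7 days) | 1 session in 3 days | 2 sessions in 3 days |
|---|---|---|---|
| 1,000 | 429 (31%) | 333 (24%) | 667 (48%) |
| 2,000 | 857 (61%) | 667 (48%) | 1,333 (95%) |
| 3,000 | 1,286 (92%) | 1,000 (71%) | 2,000 (143%) |

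**Step 4: later time contrasts in the HIT group.** From 4WK to 8WK the added steps cancel if session steps and the number of sessions in the window are alike at both visits. From 8WK to 12WK, if the 12WK wear follows the last session, the average addition of 429 to 1,286 steps/day disappears and appears as a decline.

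**Step 5: HIT against MAT.** Both arms have the same planned number, frequency and length of sessions, so the common part cancels in the group × time contrast. What remains is the difference in steps per session × 3/7. For assumed differences of 0, 250, 500 and 1,000 steps this is 0, 107, 214 and 429 steps/day.

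**Step 6: with session steps excluded,** the addition is 0 at every visit.

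**The case against.** The strongest reply is that the documents never say training continues while the monitor is worn. Testing comes after each 12-session block. Section E.6 expects about 5 months of participation, or 5 × 52/12 = 21.7 weeks, against 12 weeks of training, so pauses for testing are possible. A site could also choose training-free days or strip session steps later without breaching the text. This stands: overlap is likely at the stated frequency, but it is not established. A reader might infer that the outcome does count training as gained daily walking. The documents support only that it can.

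A reader might also infer that the HIT-MAT comparison is biased. The documents do not support that either. They give neither the size nor the direction of any difference in steps per session. Fast bursts in HIT and its recovery periods of slower walking or rest pull in opposite directions relative to heart-rate-controlled MAT.

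The percentages in the working rest on 1,400 steps/day, which Section B presents as the far end of a comparison (up to 75% fewer steps than sedentary older adults). They shrink if trial participants walk more than that.

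Finally, daily walking is a minor measure. The testing section introduces its measures as ones that may be used, the SAP leaves this one off its named secondary list, and Aim 2 is framed around walking capacity. This limits the consequence. It does not supply the missing rule, because the optional step counts that could solve the problem are not linked to the outcome.

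**Conclusion.** The point holds as a weakness in one outcome definition. Followed as written, daily walking activity can include study sessions at 4WK and 8WK, cannot at PRE, and may not at 12WK.

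If training runs on alternate weekdays through the wear period and a session yields 1,000 to 3,000 steps, the average effect on within-arm change from PRE is about 430 to 1,290 steps/day. A false 8WK-to-12WK decline of the same size is possible in the HIT group, on the further condition that the 12WK wear follows the last session. If training pauses for wear, or wear days avoid sessions, the effect is zero. The effect on the between-arm contrast is 0 to 429 steps/day for an assumed difference of 0 to 1,000 steps per session, with unknown sign.

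The 6-minute walk analysis and the four secondary outcomes named in the SAP are untouched, so this is no ground for doubting the trial's main conclusions on intensity or duration. It is worth correcting because the remedy is cheap and any reported time course of daily walking would otherwise be hard to interpret.

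**What to change.** In Blinded Outcome Testing, define daily walking activity as steps taken outside study training sessions and study testing visits, or as steps on non-training days only. Apply the same rule at PRE, 4WK, 8WK and 12WK, and state where the wear window lies relative to the testing visit. The training schedule need not change.

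Session time can be removed with recorded session start and stop times, or by subtracting the session step counts described under Intervention fidelity measures. Those counts are already planned for the same leg but are optional, so they would have to be required on wear days if that route is chosen. The documents do not describe logging of session times, so whether data already collected can be corrected depends on what the sites recorded.

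The SAP should also say whether daily walking activity is a secondary outcome under false discovery rate control or an exploratory one.

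The cost is a sentence or two of text and a filter in data processing. The downside is slightly less wear time, so some participants may need an extra wear day to reach three valid days.

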H_{1a} will be tested by the significance of the [group x time] contrast from Baseline to POST-4wk for the 6-minute walk test at $\alpha=0.05$. For H_{1b}, secondary outcomes will be tested separately using the same model as H_{1a} to identify the most sensitive measures to carry forward into future studies.¹¹⁰ The Benjamini-Hochberg procedure²²³ will be used to control the false discovery rate (FDR) for the secondary outcomes.

Aim 2: Determine the minimum locomotor training duration needed to maximize immediate effects

Hypothesis 2a (H_{2a}): Within the HIT group, *walking capacity* (6 minute walk test distance) and *secondary outcomes* will significantly increase from 4WK to 8WK and from 8WK to 12WK

Hypothesis 2b (H_{2b}): Compared to MAT, HIT will elicit significantly greater improvements in *walking capacity* and *secondary outcomes* from PRE to 8WK and from PRE to 12WK

H_{2a} will be tested by the significance of the respective time contrasts within the HIT group. **H_{2b}** will be tested by the significance of the respective [group x time] contrasts. Secondary outcomes will have FDR control.²²³

Data and Safety Monitoring Plan

An adverse event (AE) is an undesired medical occurrence in a participant who is undergoing study procedures and does not necessarily have a causal relationship with the treatment or study procedures. This includes any adverse clinical change that occurs at any time following consent. A serious AE (SAE) is any adverse experience occurring during study participation that results in any of the following outcomes: death; a life threatening situation; inpatient hospitalization or prolongation of existing hospitalization; a persistent or significant disability/incapacity.^{209,210} The data and safety monitoring plan for this study will include participant monitoring for AEs and other problems, review of AEs and other problems by the study team and IRB, and an independent data safety monitoring board (DSMB).

Participant safety monitoring

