Based on safety data from our preliminary studies^{9,12} and the extensive previous HIT research among persons with heart disease,^{65,72,76,77,98-101} and MAT research among persons post-stroke,³³ we expect a similar rate of non-serious adverse events (AEs) between HIT and MAT (e.g. temporary exercise-related soreness and fatigue), without any study-related serious AEs. As in our previous studies, we will systematically monitor for AEs. Each study visit, participant voluntary reporting of AEs will be encouraged and AEs of interest will be specifically queried, including: falls, injuries, faintness, pain and fatigue. During training, safety monitoring will include HR, blood pressure, and continuous observation for other signs or symptoms of cardiorespiratory insufficiency, worsening neurologic impairments or orthopedic injury, using accepted stopping criteria.^{142,208} AEs will be followed until resolution and categorized according to type and severity (grade 1-5),^{209,210} causal relationship with the intervention (yes/possibly/no) and whether anticipated (listed in the protocol / informed consent form or expected in the target population).

Reporting and review of AEs and other problems involving risk

All observed or volunteered AEs and other problems involving risk to research participants or others that occur throughout the study will be recorded and reported to the IRB according to UC IRB protocol, as well as reported to the DSMB (see further information about the DSMB below).. As such, all *unanticipated* AEs and other problems involving risk will be reported to the IRB and DSMB within 10 days of study staff knowledge of the event. AEs or other problems resulting in temporary or permanent interruption of the study activities by the PI to avoid potential harm to participants will be reported to the IRB and DSMB immediately (within 48 hours). Other AEs or study problems will be reported to the IRB at the time of continuing review and to the DSMB at least annually. AEs will be discussed between site PIs during regular conference calls. Withdrawal from the study and modifications to study procedures as a result of an AE or because of therapeutic measures taken to treat an AE will be at the discretion of the site PIs, in consultation with the study physicians as appropriate.

Data safety monitoring board (DSMB)

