electronic medical records system and databases of local hospitals and clinics, as in our previous UC IRB approved studies (e.g. 2013-7676, 2016-1916). We are requesting a HIPAA waiver for this purpose, as in our previous studies. For any potential participants who are identified solely by medical record review, we will only initiate a call to the participant if they have had a clinical encounter with one of the study investigators. Otherwise, we will initiate contact by mailing the participant an IRB approved flier (with the envelope addressed to "Current Resident") or by emailing an IRB approved flier to the email address(es) listed in their medical records (with the email address blind carbon copied).

For persons interested in participating, we will further explain the study, confirm initial eligibility and perform informed consent. After a research staff member explains the purpose of study and the consent, potential participants will be given the option to wait at least 24 hours to decide if they want to participate. During this consenting process, the potential participant will be provided a copy of the consent form. Standardized questions will be asked to ensure that the potential participant understands the study before consenting. HIPAA authorization will also be obtained as part of the consent process. Incorporated into the consent document is the option to agree to or refuse to participate in video recording or photographs of research activities that may be used for educational or training purposes apart from the collection of research data.

G. RISK/BENEFIT ASSESSMENT

G.1. Potential Risks

As with any exercise, there is risk of discomfort, soreness and fatigue associated with participation as well as a very low risk of musculoskeletal injury, skin abrasion and cardiovascular events.¹⁴² There is also very low potential risk of falling during clinical outcome testing and training. There may also be a risk of faintness, especially if the participant is dehydrated or does not eat on the day of exercise. Finger stick blood sampling for lactate measurement may cause a small amount of pain. Mild bruising or scarring is possible, but atypical. The risk of local infection is very low.

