Table 7. Adverse Events (AEs) in Pilot RCT

Data reported as no. of participants with AE (total no. of AEs) [AE incidence rate per 100 sessions]

	HIT (n=13, sessions=141)	MAT (n=5, sessions=60)	HIT/MAT AE odds ratio (95% CI)
Any AE	9 (21) [14.9]	4 (8) [13.3]	1.14 (0.47-2.73)
Related to intervention	6 (13) [9.2]	1 (4) [6.7]	1.42 (0.44-4.55)
-Grade 1 (mild)	5 (10) [7.1]	1 (3) [5.0]	1.45 (0.38-5.47)
-Grade 2 (moderate)	2 (3) [2.1]	1 (1) [1.7]	1.28 (0.13-12.59)
-Grade 3-5 (severe-death)	0 (0) [0.0]	0 (0) [0.0]	N/A
-Cardiac disorder	0 (0) [0.0]	0 (0) [0.0]	N/A
-Joint/muscle pain	5 (8) [5.7]	1 (4) [6.7]	0.84 (0.24-2.91)
-Fatigue	3 (3) [2.1]	0 (0) [0.0]	3.03 (0.15-59.56)*
-Nausea	0 (0) [0.0]	0 (0) [0.0]	N/A
-Lightheadedness	1 (2) [1.4]	0 (0) [0.0]	2.15 (0.10-45.43)*
-Other nervous system	0 (0) [0.0]	0 (0) [0.0]	N/A
-Fall	0 (0) [0.0]	0 (0) [0.0]	N/A
-Other injury	0 (0) [0.0]	0 (0) [0.0]	N/A
Unrelated to intervention	6 (8) [5.7]	3 (4) [6.7]	0.84 (0.24-2.91)
-Grade 1 (mild)	5 (7) [5.0]	2 (2) [3.3]	1.51 (0.31-7.51)
-Grade 2 (moderate)	1 (1) [0.7]	2 (2) [3.3]	0.21 (0.02-2.33)
-Grade 3-5 (severe-death)	0 (0) [0.0]	0 (0) [0.0]	N/A
-Atrial fibrillation	1 (2) [1.4]	0 (0) [0.0]	2.15 (0.10-45.43)*
-Other cardiac disorder	0 (0) [0.0]	0 (0) [0.0]	N/A
-Joint/muscle pain	2 (2) [1.4]	1 (2) [3.3]	0.42 (0.06-3.03)
-Fatigue	1 (1) [0.7]	0 (0) [0.0]	1.28 (0.05-31.86)*
-Nausea	0 (0) [0.0]	0 (0) [0.0]	N/A
-Lightheadedness	1 (1) [0.7]	0 (0) [0.0]	1.28 (0.05-31.86)*
-Other nervous system	0 (0) [0.0]	0 (0) [0.0]	N/A
-Fall	1 (1) [0.7]	2 (2) [3.3]	0.21 (0.02-2.33)
-Other injury	1 (1) [0.7]	0 (0) [0.0]	1.28 (0.05-31.86)*

AE odds ratios are from logistic regression modeling of no. of AEs / no. of sessions per participant. CI, confidence interval. *Continuity corrected by adding 0.5 AEs to each group so that AE odds ratios could be calculated. HIT, high-intensity interval training; MAT, moderate-intensity aerobic training

Emergency Response Planning. Although we expect that the study will be safe, we are also well prepared for any unlikely events. AEs will be promptly reported to the IRB and DSMB (see Data and Safety Monitoring Plan above) and referrals for follow up care will be made according to the severity and type of event. Should an emergency medical situation occur during study activities, emergency medical care would be provided and the participant would be transported to the nearest emergency room.

G.2. Potential Benefits

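### Seriousness does not trigger expedited reporting, so a serious adverse event classed as anticipated, with no interruption of study activities, need not reach the DSMB until a report due at least annually

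*Protocol*

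**What the plan says.** The protocol's Data and Safety Monitoring Plan defines seriousness by outcome: "A serious AE (SAE) is any adverse experience occurring during study participation that results in any of the following outcomes", followed by death, a threat to life, new or prolonged hospitalization, and lasting or significant disability.

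The subsection on reporting and review of AEs then sets three routes:

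- **10 days.** "all *unanticipated* AEs and other problems involving risk will be reported to the IRB and DSMB within 10 days of study staff knowledge".
- **48 hours, to the IRB and DSMB.** "AEs or other problems resulting in temporary or permanent interruption of the study activities by the PI to avoid potential harm to participants".
- **Everything else.** "Other AEs or study problems will be reported to the IRB at the time of continuing review and to the DSMB at least annually".

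Under Participant safety monitoring, each event is also categorized by type, severity grade, causal relationship and "whether anticipated (listed in the protocol / informed consent form or expected in the target population"). Of these, only anticipation affects a deadline.

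Section G.1 (Potential Risks) lists "a very low risk of musculoskeletal injury, skin abrasion and cardiovascular events", and also names falling. Section B describes this population as having a very high long-term risk of cardiac events and recurrent stroke. Under Emergency Response Planning, section G.1 says "AEs will be promptly reported to the IRB and DSMB" and refers back to the Data and Safety Monitoring Plan. The DSMB is to meet about once a year at a minimum. The SAP covers the between-group comparison of SAEs and sets no reporting timeline.

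**The concern.** The reporting clock depends on whether an event was anticipated and whether the PI interrupted study activities. It does not depend on how serious the event was. Both triggers rest on the study team's judgment, so the independent board's early notice of a serious event depends on decisions made by the people it oversees.

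The intervention is walking in bursts at speeds up to the fastest safe speed, in people with vascular disease. The serious events of most interest to a safety board are cardiovascular events and injury from falls. These are also the kinds of event the protocol lists as risks, which makes an anticipated classification available for them. A listed serious event could therefore be reported to the DSMB much later than a trivial event that nobody had listed. New participants would continue to be randomized to both arms in the meantime.

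**Working it through.** The plan gives no figure to reproduce. The check assigns each kind of event to a route and then sizes the gap.

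**Step 1. Assign events to routes**, using the rules in the reporting subsection.

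| Event | PI interrupts study activities? | Latest time to the DSMB |
|---|---|---|
| Any event, serious or not, anticipated or not | Yes | 48 hours |
| Unanticipated, serious or not | No | 10 days |
| Anticipated, non-serious | No | Next report, due at least annually |
| Anticipated, serious | No | Next report, due at least annually |

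The last two rows share a deadline, and seriousness changes no cell in the table.

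**Step 2. Is the last row a realistic case?** An event counts as anticipated if it is listed in the protocol or consent form, or is expected in the target population. Cardiovascular events, musculoskeletal injury and falls meet the listing limb through section G.1. Cardiac events and recurrent stroke could be argued to meet the population limb through section B. A hospitalization for one of these away from training, with no pause ordered by the PI, is the clearest example.

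**Step 3. Does other text close the gap?**

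- The Safety Data Analysis sections of the protocol and SAP describe SAEs as unexpected. That wording introduces an analysis and sets no deadline.
- The IRB's own protocol is invoked for reports to the IRB. The DSMB deadlines are stated here.
- Site PIs discuss AEs on regular calls, but those calls do not inform the DSMB.

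**Step 4. Size of the delay**, taking reports exactly 12 months apart (the minimum frequency).

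- Longest delay: about 12 months, for an event just after a report.
- Average delay, if events fall evenly between reports: 12 / 2 = 6 months.
- Ratio of the longest delay to the 10-day route: 365 / 10 = 36.5.
- One participant's involvement is about 5 months (section E.6). Someone could enter and finish within either delay.

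**Step 5. Enrolment during the delay.** Inputs are 50 to 75 participants (section F.1) and about 5 years overall (section E.6). Even accrual over those 5 years is my assumption.

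- Per 12 months: 50 / 5 = 10 to 75 / 5 = 15 participants.
- Per 6 months: 10 / 2 = 5 to 15 / 2 = 7.5 participants.

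If enrolment takes less than the full 5 years, the yearly number rises.

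**The case against.** There is a fair case on the other side, and parts of it stand.

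- **The 48-hour route may be wide.** A reader might infer that only stopping the whole trial triggers it. The text does not say so. It covers temporary as well as permanent interruption of study activities, and pausing one participant could qualify. On that reading many SAEs during training would be reported within 48 hours. The remaining gap is an SAE with no pause by the PI, typically away from training.
- **The anticipated class is arguable.** A reader might infer that every serious cardiac event, recurrent stroke or fall injury is anticipated by definition. The documents do not settle this. The protocol expects no study-related SAEs, and both documents call an SAE unexpected, so staff could reasonably choose the 10-day route. Recurrent stroke is not named in the G.1 risk list, and the statement in section B concerns long-term risk. The listing limb still points the other way for cardiovascular events, falls and injury.
- **Section G.1 is not a rival rule.** It is tempting to call its promise of prompt reporting a flat contradiction. The sentence sits under emergency planning and defers to the monitoring plan for detail. Read literally, it would also require prompt reporting of mild soreness. It is loosely worded, but an annual default still fits badly with the word promptly.
- **Annual is a minimum.** A reader might infer that the DSMB could not act between meetings, or that the delay is always 12 months. Both the reporting and the meeting frequencies are floors. Earlier notice is allowed, but it is not required in this case.
- **The IRB side cannot be judged.** Its policy is not among the documents and may be stricter.

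These points narrow the gap. None of them sets a DSMB deadline for an anticipated SAE without interruption.

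**Conclusion.** The point holds in a limited form. The reporting rules leave one class of SAE, anticipated and without interruption of study activities, on the slowest route to the DSMB. The delay can reach about 12 months and averages about 6 if events fall evenly between annual reports. A minor unanticipated event must be reported within 10 days. Up to about 10 to 15 people would be enrolled over the longest delay, assuming even accrual of 50 to 75 participants over 5 years. Those figures count enrolments and not harm, because the documents give no expected SAE rate.

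The conclusion rests on reading the definition of anticipated as written and the annual frequency as all that the protocol guarantees. It does not affect the efficacy analysis. I would treat it as a cheap improvement to safety oversight.

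**What to change.** Amend the reporting subsection of the Data and Safety Monitoring Plan as follows:

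1. State that every SAE, anticipated or not and related or not, is reported to the DSMB no later than the existing 10-day route, or within 48 hours if study activities are interrupted, and to the IRB as its policy requires.
2. State whether interruption of study activities includes pausing a single participant.
3. Keep the annual route for anticipated events that are not serious.
4. Align the reporting sentence under Emergency Response Planning in section G.1 with these rules.

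The cost is a short amendment and a few extra expedited reports. The burden should be small, since the protocol expects no study-related SAEs and treats any SAE as unexpected. Including unrelated and anticipated SAEs is a choice of convention that nothing in the documents requires. Its advantage is that the DSMB deadline for a serious event no longer depends on how the study team classifies it.
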